12.7.1.1 Statistical Hypotheses

No hypothesis testing of the primary safety endpoints is planned.

12.7.1.2 Analysis Methods

The SAF will be used for this analysis. The number and percentage of eyes experiencing each of the primary safety endpoints will also be calculated. The safety criteria will be considered to have been met if the percentage is less than the target rate at the time of refractive stability for all of the primary safety endpoints.

12.8 Interim Analyses and Reporting

An analysis will be performed once refractive stability is achieved; a final analysis will be performed once the one year follow-up is complete.

12.9 Sample Size Justification

Up to 374 eyes will be treated in this study. With 374 eyes treated, any ocular serious adverse event type that occurs in at least 1% of the population undergoing the procedure will be observed in this study at least one time, with approximately 95% probability. This is in accordance with ANSI Z80.11-2012(R2017).

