Refractive stability is said to have been achieved at the latter of two postoperative manifest refractions performed at least 3 months apart (or at 3 months after surgery when compared with the 1-month visit) if all the requirements for stability listed in the endpoints section of the synopsis have been met. Stability will be confirmed by an adequate subgroup (at least 80% of the cohort) at the next scheduled visit interval.

The number and percentage of eyes meeting each of the primary effectiveness endpoints will be calculated. The effectiveness criteria will be considered to have been met if the percentage meets or exceeds the target rate at the time of refractive stability for all primary effectiveness endpoints.

The number and percentage of eyes experiencing each of the primary safety endpoints will also be calculated. The safety criteria will be considered to have been met if the percentage is less than the target rate at the time of refractive stability for all of the primary safety endpoints.

An analysis will be performed once refractive stability is achieved; a final analysis will be performed once the one-year follow-up is complete.

	Up to 374 eyes will be treated in this study. With 374 eyes treated, any ocular serious adverse event type that occurs in at least 1% of the population undergoing the procedure will be observed in this study at least one time, with approximately 95% probability. This is in accordance with ANSI Z80.11-2012(R2017).
Key Words	LASIKRay TracingMyopiaAstigmatism
Associated Materials	 WaveLight® EX500 Laser System WaveLight® FS200 Laser System Patient Interface for WaveLight FS200 Laser System WaveCard

Table 3–1 Schedule of Study Procedures and Assessments

		Screening ¹	Surgery	Surgery Postoperative								er
		Visit 0	Visit 00 / Visit 00A ²	Visit 1 / Visit 1A	Visit 2 / Visit 2A	Visit 3 / Visit 3A	Visit 4 / Visit 4A	Visit 5 / Visit 5A	Visit 6 / Visit 6A	Visit 7 / Visit 7A	Early Exit	USV ³
Proce	edure/ Assessment	Day -30 to -1	Day 0	Day 1	Day 5 to 9	Day 21 to 35	Day 70 to 98	Day 147 to 182	Day 245 to 301	Day 330 to 420		
Inform	med Consent	X										
Inclusion/Exclusion		X	X^4									
Demographics		X										
Medic	cal History	X										
Concomitant Medications		X	X	X	X	X	X	X	X	X	X	X
Urine	Pregnancy Test ⁵ *	X										
Cyclo	plegic Refraction	X						X				
Mesopic pupil size		X				X	X	X	X	X	X	
	Aberrometry	X^6				X	X	X	X	X	X	
lap	Biometry	X^6				X	X	X	X	X	X	
ghtn	Keratometry	X^6				X	X	X	X	X	X	

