6.3.1 Primary Safety Endpoints

- Percentage of eyes that lose 2 lines or more of BCDVA (Target at refractive stability $\leq 5\%$)
- Percentage of eyes with BCDVA worse than 20/40 (for eyes with BCDVA of 20/20 or better pre-op) (Target at refractive stability ≤ 1%)
- Percentage of eyes that have an increase of manifest refractive astigmatism of greater than 2.00 D of absolute cylinder as compared to the preoperative refraction (Target at refractive stability $\leq 5\%$)
- Percentage of eyes with a serious, non-flap related, ocular adverse event at the postoperative visits (Target per event type at refractive stability ≤ 1%)

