7 INVESTIGATIONAL PLAN

7.1 Study Design

This is a prospective, single-arm, multi-center, interventional study with planned bilateral InnovEyes LASIK treatment for subjects requiring refractive correction of myopia with or without astigmatism. All treated eyes will be targeted for emmetropia. The postoperative state of each treated eye will be compared to the preoperative state of the same eye.

Subjects will be evaluated initially for suitability as candidates for bilateral LASIK. Potential subjects willing to participate will be consented and screened. Approximately 187 qualified subjects (up to 374 eyes) will receive bilateral InnovEyes LASIK and be followed for 1 year. Total duration of subject participation is approximately 1 year and includes 9 study visits consisting of Screening, Surgery, 1 day, 1 week, 1 month, 3 month, 6 months, 9 months, and

12 months. Subjects will be enrolled with intent to treat at least 20 eyes in each spherical diopter and each cylindrical diopter range (with only 10 eyes in the highest cylinder bin). Approximately 10 US study sites will participate in this clinical study. It is estimated that enrollment and follow-up of all subjects will take approximately 22 months. Additional information on the study population can be found in Section 8.

Assessments will be obtained at baseline and at appropriate times after InnovEyes LASIK to evaluate the safety and effectiveness of the treatment.

The main analyses for effectiveness and safety will be conducted when refractive stability for the cohort has been determined and 80% of the eyes in the cohort have completed the next scheduled visit after refractive stability (Refractive Stability is defined in Section 6.4 and 12.4). The Sponsor may file a Pre-Market Approval application once this analysis is complete. Subjects are followed for at least 12 months (Day 330 to Day 420) for safety and supportive effectiveness assessments. Final data analyses will be conducted at study completion.

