12.2.1 Safety Analysis Set

The safety analysis set (SAF) will contain all eyes that undergo surgery or attempted surgery (defined as eye drops given for flap treatment); the SAF will be the primary analysis set for the safety analyses.

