6.1.2 Analysis Methods

The SAF will be used for this analysis. The number and percentage of eyes experiencing each of the primary safety endpoints will also be calculated. The safety criteria will be considered to have been met if the percentage is less than the target rate at the time of refractive stability

for all of the primary safety endpoints. Adverse events that are non-flap related will be indicated as such on the adverse event CRF. It should be noted that the percentage of eyes with a serious, non-flap related, ocular adverse event will be compared to the 1% target by adverse event type (not for all ocular adverse event types combined).

[figure not shown]
Summary statistics for the primary safety endpoints will be presented by site, race and ethnicity, age (> 21 years old vs. \leq 21 years old), and by gender.

[figure not shown]

[figure not shown]
Document ID: V-CLN-0000922

Page 25 of 56

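### Does the stated 95% chance of seeing a 1% adverse event among 374 eyes need correcting?

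*Protocol*

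**What the plan says.** The same statement appears in the Protocol Summary, Protocol 12.9 and SAP 7. Its premise is "With 374 eyes treated, any ocular serious adverse event type that occurs in at least 1% of the population undergoing the procedure", and its conclusion is that such an event "will be observed in this study at least one time, with approximately 95% probability". The only support cited is accordance with the ANSI standard for corneal reshaping lasers. The visible text gives no formula, no independence assumption and no fellow-eye correlation.

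Other sections bear on how to read it:

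- The number of eyes is a ceiling: "Up to 374 eyes will be treated in this study" (Protocol 12.9).
- The eyes come in pairs: "Approximately 187 qualified subjects (up to 374 eyes) will receive bilateral InnovEyes LASIK and be followed for 1 year" (Protocol 7.1).
- The unit for safety is the eye. The endpoint is "Percentage of eyes with a serious, non-flap related, ocular adverse event at the postoperative visits" (Protocol 6.3.1), the safety set holds "all eyes that undergo surgery or attempted surgery" (Protocol 12.2.1), and SAP 6.1.2 says that "the percentage of eyes with a serious, non-flap related, ocular adverse event will be compared to the 1% target by adverse event type".
- Protocol section 8 allows for up to 10% loss to follow-up and expects no fewer than 300 eyes to be treated and followed.
- Protocol 12.7.1.1 and SAP 6.1.1 plan no hypothesis test of the primary safety endpoints.

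**The concern.** The sentence supplies everything a reader needs for a one-line check: a number of eyes, a rate and a probability. The check fails, because 374 independent eyes give 97.7% and 299 would be enough for 95%. The obvious next thought is that the 95% already allows for both eyes of a subject tending to have the same complication, but no correlation is stated.

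This is the only probability in the visible sample-size text, so it carries the whole quantitative argument for the size of the study. Fellow-eye concordance is a real issue when both eyes are treated by the same surgeon with the same laser. If concordance were strong, the true chance of seeing a 1% event would be below 95%, and the plan would be promising more than it delivers. From the sentence alone a reader cannot tell whether the figure is cautious, exact or optimistic.

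**Working it through.** **Inputs.** n = 374 eyes and p = 0.01 (Protocol 12.9); m = 187 subjects with two eyes each (Protocol 7.1); up to 10% loss and a floor of 300 eyes (Protocol section 8); main analysis once 80% of eyes have completed the visit after stability (Protocol 7.1). The fellow-eye correlation ρ is not in the documents, so a range is shown.

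**1. The plan's figure as printed, independent eyes.** P(at least one) = 1 − (1 − p)^n.

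- 1 − 0.99^374 = 0.9767. The printed 95% is not reproduced; the difference is 97.7 − 95 = 2.7 points.
- Smallest n for 95%: ln(0.05)/ln(0.99) = 298.07, so 299 eyes (1 − 0.99^299 = 0.9505).
- Rate for which 374 independent eyes give exactly 95%: 1 − 0.05^(1/374) = 0.80%.

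**2. Other eye counts that the protocol itself gives, still independent.**

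| Basis | Eyes | P(at least one) |
|---|---|---|
| Ceiling | 374 | 97.7% |
| Less 10% loss (374 × 0.9 = 336.6) | 336 | 96.6% |
| Floor in section 8 | 300 | 95.1% |
| 80% of eyes (374 × 0.8 = 299.2) | 299 | 95.0% |

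The 300-eye floor reproduces the printed figure with no correlation at all. That it is the source is an inference, since 12.9 does not mention 300.

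**3. Pairs of eyes, pairwise model.** P(neither eye) = 0.99² + ρ × 0.01 × 0.99 = 0.9801 + 0.0099ρ, and P(at least one) = 1 − (0.9801 + 0.0099ρ)^187.

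| Assumed ρ | P(at least one) |
|---|---|
| 0 | 97.7% |
| 0.1 | 97.2% |
| 0.3 | 95.9% |
| 0.405 | 95.0% |
| 0.5 | 94.0% |
| 1 (bound) | 84.7% |

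The result stays within two points of 95% for ρ from 0.13 to 0.58.

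**4. Pairs of eyes, design-effect model.** Effective eyes = 374/(1 + ρ). Setting this equal to 298.07 gives ρ = 374/298.07 − 1 = 0.25. The correlation that yields 95% therefore depends on the model: about 0.40 in step 3 and about 0.25 here.

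**5. Where the figure is used.** The safety criterion in Protocol 12.7.1.2 and SAP 6.1.2 compares observed percentages with fixed targets, on the safety set. Enrolment in Protocol section 8 is set by the refractive bins, the expected screen failures and the expected loss. Neither takes the 95% as an input.

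**The case for a change.** The best case for a change is that the sentence ties its probability to 374 treated eyes and to nothing else. If 300 eyes was the basis, the sentence names the wrong number, and 95.1% still assumes independent eyes: with 150 pairs the pairwise model gives 92.8% at ρ = 0.25 and 91.0% at ρ = 0.4. Allowing only for the stated 10% loss gives 96.6%, which is not the printed value either. If the reference to a population meant subjects rather than eyes, 187 subjects at 1% would give 84.7%. Several routes to about 95% exist, they do not agree with each other, and the plan names none. One sentence in three places would settle it at almost no cost.

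Most of this stands as an observation: the basis is not stated, and the printed pair of numbers does not reproduce under independence. It does not show that the figure is wrong. The endpoint, the safety set and the comparison with 1% all count eyes, so the subject-level reading is not the natural one. The figure is described as approximate, the rate is a minimum and the number of eyes is a maximum. Replacing 95% by 97.7% would attach a less cautious number to the ceiling on enrolment, next to a statement of accordance with a standard that cannot be checked here.

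**Conclusion.** No change is needed. The mismatch is real but small: 2.7 points under independence, in the cautious direction. For the paired design the printed value sits inside the range of 84.7% to 97.7%, and it agrees with the protocol's own floor of 300 eyes (95.1%). It would overstate the chance of detection if fellow-eye correlation exceeded about 0.40 for 187 pairs in the pairwise model (about 0.25 with a design effect), or if independence failed with only 300 eyes. The documents give no correlation from which to judge this.

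What decides the matter is that nothing depends on the number. The success criteria use observed percentages, no test or power calculation rests on it, and recruitment is driven by the refractive bins. Once the data are in, the planning probability has no role: the safety results will be the observed counts of eyes by event type. Stating the assumption would be tidier, but the trial would enrol the same eyes and report the same results.

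This rests on the visible text. A figure in SAP 7 is not shown and may carry the missing detail.

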13 DATA HANDLING AND ADMINISTRATIVE REQUIREMENTS

13.1 Subject Confidentiality

The Investigator must ensure that the subject's anonymity is maintained throughout the course of the study. In particular, the Investigator must keep an enrollment log with confidential identifying information that corresponds to the subject numbers and initials of each study participant. At the end of the clinical study, the Study Sponsor will collect a copy of the enrollment log *without any identifying subject information*. All documents submitted to the Study Sponsor will identify the subjects exclusively by number and demographic information. No other personally identifying information will be transmitted to the Study Sponsor.

The Study Sponsor may release anonymized study data to external researchers for purposes of future research directly related to the study objectives, or future research that is beyond the

scope of the current study objectives. The Informed Consent Form explains this to study subjects. Anonymization means that all identifiable information will be removed from the dataset and all links to the subjects in the study will be removed. Anonymization of the data will maintain confidentiality of the subjects who participate in the study so that they cannot be identified by external researchers. The anonymized data set will contain records from all of the subjects in the current study, but the anonymization process might change the data set in some ways, so external researchers will be informed that they might not be able to duplicate some of the results from this study.

13.2 Completion of Source Documents and Case Report Forms

The nature and location of all source documents will be identified to ensure that original data required to complete the CRFs exist and are accessible for verification by the site monitor, and all discrepancies shall be appropriately documented via the query resolution process. Site monitors are appointed by the Study Sponsor and are independent of study site staff.

If electronic records are maintained, the method of verification must be determined in advance of starting the study.

At a minimum, source documents include the following information for each subject:

- Subject identification (name, sex, race/ethnicity)
- Documentation of subject eligibility
- Date of informed consent
- Dates of visits
- Documentation that protocol specific procedures were performed
- Results of study parameters, as required by the protocol
- IP accountability records
- Documentation of AEs and other safety parameters (if applicable)
- Records regarding medical histories and the use of concomitant therapies prior to and during the study
- Date of study completion and reason for early discontinuation, if applicable

It is required that the author of an entry in the source documents be identifiable. Direct access to source documentation (medical records) must be allowed for the purpose of verifying that the data recorded on the CRF are consistent with the original source data.

Only designated individuals at the site will complete the CRFs. The CRFs must be completed at regular intervals following the clinical study visit schedule. It is expected that all data reported have corresponding entries in the source documents. The Principal Investigator is responsible for reviewing and certifying that the CRFs are accurate and complete. The only subject identifiers recorded on the CRFs will be subject number, and subject demographic information.

The Sponsor reserves the right to collect anonymized raw data from the InnovEyes sightmap or InnovEyes software at any point of the study and at the end of the study in order to use for further review of the treatment results and for future development of the procedure.

13.3 Data Review and Clarifications

A review of CRF data to the subject's source data will be completed by the site monitor to ensure completeness and accuracy. After the CRFs have been completed, additional data clarifications and/or additions may be needed as a result of the data cleaning process. Data clarifications are documented and are part of each subject's CRF.

13.4 Sponsor and Monitoring Responsibilities

The Study Sponsor will designate a monitor to conduct the appropriate site visits at the appropriate intervals according to the study monitoring plan. The clinical investigation will be monitored to ensure that the rights and well-being of the subjects are protected, the reported data are accurate, complete, and verifiable from the source documents, and the study is conducted in compliance with the current approved protocol (and amendments[s], if applicable), with current GCP, and with applicable regulatory requirements.

The site may not screen subjects or perform the informed consent process on any subject until it receives a notification from an appropriate Study Sponsor representative that the site may commence conducting study activities. Monitoring will be conducted periodically while the clinical study is ongoing. Monitoring methods may include site visits, telephone, written, and

email correspondence. Close-out visits will take place after the last visit of the last subject at the site.

A Coordinating Investigator may be identified by the Study Sponsor to review and endorse the final study report. In cases where a Coordinating Investigator is engaged, the Study Sponsor will select the Coordinating Investigator based upon their experience, qualifications, active study participation, and their willingness and availability to take on this role.

Additionally, Alcon may have an expert Sponsor Representative present during screening (eg, for the collection of InnovEyes sightmap measurements) or surgery to offer training to the Investigator on proper operation of the device and/ or to make technical observations during the study visit.

• The Sponsor Representative must be supervised by the Investigator or designee to ensure the Sponsor Representative's presence or activities do not bias the outcome of the study, affect the quality of the research data, and/or compromise the rights and welfare of the subject. The Sponsor Representative will not intervene with the standard of care provided to study subjects or make safety-related decisions or assessments. The activities of Sponsor Representatives will be described in the Informed Consent.

13.5 Regulatory Documentation and Records Retention

The Investigator is required to maintain up-to-date, complete regulatory documentation as indicated by the Study Sponsor and the Investigator's files will be reviewed as part of the ongoing study monitoring. Financial information is to be kept separately.

Additionally, the Investigator must keep study records and source documents consistent with the terms of the clinical study agreement with the Study Sponsor. If the Investigator retires, relocates, or for any other reason withdraws from responsibility of keeping the study records, then the Study Sponsor must be notified and suitable arrangements made for retention of study records and source documents needed to comply with national and international regulations.

13.6 Quality Assurance and Quality Control

The Study Sponsor will secure agreement from all involved parties to ensure direct access to all study related sites, source data and documents, and reports for the purpose of monitoring and auditing by the Study Sponsor, and inspection by domestic and foreign regulatory authorities. Quality control will be applied to each stage of data handling to ensure that all data are reliable and have been processed correctly. Agreements made by the Study Sponsor

with the Investigator/Institution and any other parties involved in the clinical study will be provided in writing as part of the protocol or as a separate agreement.

14 ETHICS

This clinical study must be conducted in accordance with the ethical principles contained within:

- The Declaration of Helsinki, and in compliance with the ICH E6 GCP Consolidated Guideline, ISO 14155:2011, and the applicable US FDA 21 CFR Regulations.
- SOPs of the Study Sponsor and contract research organizations participating in the conduct of the clinical study and all other applicable regulations.
- Notifications and timelines for reporting protocol deviations should be based upon applicable Ethics Committee requirements

The Investigator must ensure that all personnel involved in the conduct of the study are qualified to perform their assigned responsibilities through relevant education, training, and experience. The Investigator and all clinical study staff must conduct the clinical study in compliance with the protocol. Deviations from this protocol, regulatory requirements, and/or GCP must be recorded and reported to the Sponsor prior to database lock. If needed, corrective and preventive action should be identified, implemented, and documented within the study records. Use of waivers to deviate from the clinical protocol is prohibited.

Before clinical study initiation, this protocol, the informed consent form, any other written information given to subjects, and any advertisements planned for subject recruitment must be approved by an IRB/IEC. The Investigator must provide documentation of the IRB/IEC approval to the Study Sponsor. The approval must be dated and must identify the applicable protocol, amendments (if any), informed consent form, assent form (if any), all applicable recruiting materials, written information for subject, and subject compensation programs. The IRB/IEC must be provided with a copy of the InnovEyes sightmap investigator brochure, any periodic safety updates, and all other information as required by local regulation and/or the IRB/IEC. At the end of the study, the Investigator must notify the IRB/IEC about the study's completion. The IRB/IEC also must be notified if the study is terminated prematurely. Finally, the Investigator must report to the IRB/IEC on the progress of the study at intervals stipulated by the IRB/IEC.

Voluntary informed consent must be obtained in writing from every subject and the process shall be documented before any procedure specific to the clinical investigation is applied to

the subject. The Investigator must have a defined process for obtaining consent. Specifically, the Investigator, or their delegate, must explain the clinical study to each potential subject and the subject must indicate voluntary consent by signing and dating the approved informed consent form. The subject must be provided an opportunity to ask questions of the Investigator, and if required by local regulation, other qualified personnel. The Investigator must provide the subject with a copy of the consent form written in a language the subject understands. The consent document must meet all applicable local laws and provide subjects with information regarding the purpose, procedures, requirements, and restrictions of the study, along with any known risks and potential benefits associated with the IP and the study, the available compensation, and the established provisions for maintaining confidentiality of personal, protected health information. Subjects will be told about the voluntary nature of participation in the study and must be provided with contact information for the appropriate individuals should questions or concerns arise during the study. The subject also must be told that their records may be accessed by appropriate authorities and Sponsor-designated personnel. The Investigator must keep the original, signed copy of the consent (file in subject's medical records) and must provide a duplicate copy to each subject according to local regulations.

The Study Sponsor assures that the key design elements of this protocol will be registered on www.clinicaltrials.gov as required by current regulations and, if applicable, other public databases as required by local country regulations. In addition, results of this study will be made publicly available on www.clinicaltrials.gov regardless of outcome as required by current regulations and, if applicable, in other public databases as required by local country regulations.

